6.7.5. Vital Signs

Where supine blood pressure is measured in triplicate, the mean value will be calculated and used in all subsequent calculations. When triplicate blood pressure measurements precede a standing measurement, the last supine blood pressure measurement will be used for orthostatic calculations. Orthostatic values will be calculated as the standing value minus the last supine value taken prior to the standing value.

Vital signs data for individual patients will be listed by time point. Vital signs data will also be summarized at each time point by body weight category and age category, together with changes from baseline for supine vital signs. For supine vital signs, baseline is defined as the mean of the triplicate measurement taken at predose. Figures of mean vital signs and mean changes from baseline profiles will be presented by cohort and region over time.

Counts and percentages of patients displaying categorical shifts (as given by the criteria in [Table LAHX.6.1](#)) will be summarized by body weight category. [Table LAHX.6.1](#) displays the Lilly-defined criteria for categorical shifts for supine blood pressure, pulse, and orthostatic blood pressure. The last column of the table displays the patient populations defined by baseline categories.

Table LAHX.6.1. Criteria for Categorical Shifts in Vital Signs

Parameter	Age Group	Direction	Criteria	Patient Population defined by Baseline Categories
Systolic BP (mm Hg) (supine)	6-9	Low	≤ 80 and decrease ≥ 15	> 80
		High	≥ 122 and increase ≥ 15	< 122
	10-11	Low	≤ 85 and decrease ≥ 20	> 85
		High	≥ 126 and increase ≥ 20	< 126
	12-14	Low	≤ 90 and decrease ≥ 20	> 90
		High	≥ 136 and increase ≥ 20	< 136
	15-17	Low	≤ 90 and decrease ≥ 20	> 90
		High	≥ 140 and increase ≥ 20	< 140
Diastolic BP (mm Hg) (supine)	6-9	Low	≤ 45 and decrease ≥ 10	> 45
		High	≥ 78 and increase ≥ 10	< 78
	10-11	Low	≤ 50 and decrease ≥ 10	> 50
		High	≥ 82 and increase ≥ 10	< 82
	12-14	Low	≤ 50 and decrease ≥ 10	> 50
		High	≥ 86 and increase ≥ 10	< 86
	15-17	Low	≤ 50 and decrease ≥ 10	> 50
		High	≥ 90 and increase ≥ 10	< 90
Pulse (bpm) (supine)	6-9	Low	< 60 and decrease ≥ 25	≥ 60
		High	> 150 and increase ≥ 25	≤ 150
	10-11	Low	< 60 and decrease ≥ 25	≥ 60
		High	> 140 and increase ≥ 25	≤ 140
	12-14	Low	< 50 and decrease ≥ 15	≥ 50
		High	> 120 and increase ≥ 15	≤ 120
	15-17	Low	< 50 and decrease ≥ 15	≥ 50
		High	> 100 and increase ≥ 15	≤ 100
Systolic BP (mm Hg) (orthostatic)	All	Decrease	Decrease ≥ 20	All patients
Diastolic BP (mm Hg) (orthostatic)	All	Decrease	Decrease ≥ 10	All patients

Abbreviations: BP = blood pressure; bpm = beats per minute; mm Hg = millimeters of mercury.

Note: "all patients" include all safety analysis patients with both a non-missing baseline (predose) measure and at least 1 non-missing postbaseline measure.

Beasley and Moscarelli 2015.

The criteria consist of 2 parts, an absolute threshold and a change from baseline (predose) amount.

- The absolute threshold in the criteria is based on: 1) minimum postbaseline when the direction is low; 2) maximum postbaseline when the direction is high.
- The change from baseline amount in the criteria is: 1) decrease from non-missing baseline to minimum postbaseline when the direction is low; 2) increase from non-missing baseline to maximum post baseline when the direction is high.

6.7.6. *Electrocardiograms*

Any clinically significant electrocardiogram (ECG) finding that results in a diagnosis and that occurs after the patient receives lasmiditan will be reported as an AE.

Counts and percentages displaying shifts from normal, abnormal (not clinically significant), or abnormal (clinically significant) at baseline (predose) to normal, abnormal (not clinically significant), or abnormal (clinically significant) at 24 hours postdose will be summarized. Baseline is defined as ECG findings taken at predose.

Descriptive statistics will be presented separately by body weight category and age category.

6.7.7. *Cognition*

Data for the following Cogstate Pediatric Brief Battery parameters will be listed by time point:

- Detection Test score: mean of the \log_{10} transformed reaction times for correct responses
- Identification Test score: mean of the \log_{10} transformed reaction times for correct responses
- One Back Test score: mean of the \log_{10} transformed reaction times for correct responses
- One Card Learning Test score: arcsine transformation of the square root of the proportion of correct responses

For each test score, listings will also include change from baseline (predose) and the reliable change index (RCI) score at each post-dose time point, which will be computed as follows:

$$RCI = \frac{score_{post} - score_{baseline}}{s_{norm}\sqrt{2(1-r)}} \times Multiplicand$$

where:

- $score_{post}$ = patient's score at the given post-dose time point
- $score_{baseline}$ = patient's score at baseline
- s_{norm} = population standard deviation from age-matched normative data
- r = normative test-retest reliability
- $Multiplicand$ = -1 for the Detection, Identification, and One Back tests
= +1 for the One Card Learning test

The number and percent of patients with at least 2 RCI scores less than or equal to -1.65 will be reported and summarized by age category at each postdose time point (Ingraham and Aiken 1996; Louey et al. 2014). Age-specific normative s_{norm} and r values for each test are provided in [Appendix 1](#) (Cromer et al. 2015; Hammers et al. 2012; Mollica et al. 2005; Rosenfeld et al. 2018; Yoshida et al. 2011).

Descriptive statistics for the Detection, Identification, One Back, and One Card Learning test scores, together with changes from baseline, will be presented by age category at each time point. For each test score, the Cohen's d effect size measure (Cohen 1988) will also be computed at each postdose time point as follows:

$$d = \frac{mean_{change,cat,1} - mean_{change,cat,2}}{s_{change}}$$

where:

- $mean_{change,cat,i}$ = mean change from baseline for the i^{th} age category ($i = 1 \rightarrow 6$ to <12 years of age; $i = 2 \rightarrow 12$ to <18 years of age)
- s_{change} = standard deviation of change from baseline values, pooled across the 2 age categories

6.7.8. Safety Topics of Interest

This section includes areas of interest whether due to observed safety findings, potential findings based on drug class, or requested by a regulatory agency for any reason.

Standardized MedDRA Queries (SMQs) are groupings of terms from 1 or more MedDRA SOCs that relate to a defined medical condition or area of interest. When an SMQ is specified, the resulting tabular display will include counts and percentages by treatment group at the SMQ level and at the PT level within the SMQ. When an SMQ involves both narrow and broad terms, the summaries will occur at the SMQ level, then the narrow/broad level, and subsequently the PT level within the SMQ.

6.7.8.1. Evaluation of Cardiovascular Safety

Definitions of Lilly Search Categories (LSCs) for cardiovascular (CV) events:

1. Potential CV AEs: all PTs (for TEAEs and AEs) in the SMQs listed below plus PTs of abdominal pain, abdominal pain upper, and abdominal pain lower.
2. Likely CV AEs: a subset of the potential CV AEs. All clinical information from patients who reported the PT events identified from the search described above for potential CV AEs will undergo medical review and medical judgment will be applied to determine if the AE (for each patient) was likely CV in nature. If so, it will be defined as a likely CV AE.

SMQs:

- broad and narrow terms in cardiac arrhythmias (includes sub SMQs) (SMQ 20000049)
- broad and narrow terms in cardiac failure (SMQ 20000004)
- broad and narrow terms in cardiomyopathy (SMQ 20000150)
- broad and narrow terms in central nervous system vascular disorders (includes sub SMQs) (SMQ 20000060)
- broad and narrow terms in embolic and thrombotic events (includes sub SMQs) (SMQ 20000081)
- broad and narrow terms in hypertension (SMQ 20000147)

- broad and narrow terms in ischemic heart disease (includes sub SMQs) (SMQ 20000043)
- broad and narrow terms in pulmonary hypertension (SMQ 20000130)
- broad and narrow terms in Torsade de pointes/QT prolongation (SMQ 20000001)

Patient narratives will be provided for patients with potential and likely CVs, likely CV SAEs, and likely CV AEs leading to discontinuations.

6.7.8.2. Evaluation of Hepatic Safety

Refer to Section 6.7.4.2 for a description of hepatic analyses.

6.7.8.3. Evaluation of Injuries and Accidents Secondary to Neurologic Adverse Events

The number and percentage of patients with at least 1 TEAE in the ‘Nervous System Disorders’ SOC and/or at least 1 AE in the ‘Injury, Poisoning, and Procedural Complications’ SOC will be summarized.

Among patients with at least 1 AE in the ‘Injury, Poisoning, and Procedural Complications’ SOC, the number and percentage of patients who reported AEs in this SOC will be summarized, using MedDRA PTs listed by decreasing frequency in the total population. For each AE in this summary, the number and percentage of patients who reported at least 1 TEAE in the ‘Nervous System Disorders’ SOC will also be summarized. Descriptive statistics will be presented separately by body weight category and age category.

Outcomes will be evaluated by medical review of any other AEs (for example, falls, fractures, sprains, head injury) reported when the patients experienced neurologic-related events. Patient narratives for patients with adverse functional outcomes associated with neurologic-related events will be provided based on medical review that includes the neurologic-related events and any other AEs indicative of an adverse outcome that could be potentially related to the neurological TEAE.

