6.7. Safety and Tolerability Assessments

6.7.1. Adverse Events

Where changes in severity are recorded in the Case Report Form (CRF), each separate severity of the AE will be reported in the listings, only the most severe will be used in the summary tables. A pre-existing condition is defined as an AE that starts before the patient has provided written informed consent and is ongoing at consent. A treatment-emergent AE (TEAE) is defined as an AE which occurs postdose or which is present prior to dosing and becomes more severe postdose. A non-treatment emergent AE (non-TEAE) is defined as an AE which starts after informed consent but prior to dosing.

All AEs occurring on or after the date of informed consent form signing, discontinuations due to AEs, pre-existing conditions and medical history, serious AEs, and serious TEAEs will be listed.

The number and percentage of patients who report TEAEs will be summarized using preferred terms (PTs) from the most current version of Medical Dictionary for Regulatory Activities (MedDRA), where PTs will be nested within system organ class (SOC). System organ classes will be listed alphabetically and PTs within each SOC will be listed by decreasing frequency in the total population. The number and percentage of patients who report TEAEs will also be summarized using MedDRA PTs listed by decreasing frequency in the total population.

The number and percentage of patients with TEAEs by maximum severity will be summarized using MedDRA PTs listed by decreasing frequency in the total population. For each patient and TEAE, the maximum severity for the MedDRA PT is the maximum post-baseline severity observed from all associated lower level terms mapping to the MedDRA PT. The maximum severity will be determined based on the non-missing severities. If all severities are missing for the defined postbaseline period of interest, it will show as missing in the table.

The number and percentage of patients with TEAEs that are related to study drug will be summarized using MedDRA PTs listed by decreasing frequency in the total population. Related TEAEs are those that are recorded on the AE CRF page as related to study treatment or those with a missing relationship.

For events that are gender-specific, the denominator and computation of the percentage will include only patients from the specific gender.

Descriptive statistics will be presented separately by body weight category and age category.

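### SAP 6.7.8.3 counts any injury AE against neurologic TEAEs; where onset is known, this adds only predose, non-worsened injuries, which cannot follow the postdose neurologic event

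*SAP*

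**What the plan says.** The section is headed "Evaluation of Injuries and Accidents Secondary to Neurologic Adverse Events". It plans three things.

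- **First summary.** Patients with at least one TEAE in the Nervous System Disorders class "SOC and/or at least 1 AE in the" Injury, Poisoning, and Procedural Complications class.
- **Second summary.** It is restricted to the injury group ("Among patients with at least 1 AE in the" injury class), with rows "using MedDRA PTs listed by decreasing frequency in the total population". Within it is a cross-tabulation: "For each AE in this summary, the number and percentage of patients who reported at least 1 TEAE in the" nervous system class.
- **Medical review and narratives.** The review looks at other AEs "reported when the patients experienced neurologic-related events".

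The terms are defined in SAP 6.7.1: "A treatment-emergent AE (TEAE) is defined as an AE which occurs postdose or which is present prior to dosing and becomes more severe postdose". The complement is also defined: "A non-treatment emergent AE (non-TEAE) is defined as an AE which starts after informed consent but prior to dosing". A condition that began before consent and is still present at consent is called pre-existing, and 6.7.1 classes it as a kind of AE. Section 6.7.1 also lists all AEs from consent onward, and pre-existing conditions. SAP 5.1 describes a single dose.

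**The concern.** The section's purpose is to show harm that may result from a neurologic effect of the drug. The two sides of the count nevertheless use different time frames: the neurologic event must be treatment-emergent, but the injury need not be. A sprain that occurred between consent and dosing, and did not worsen, enters the same tables as a fall after dosing. From the counts alone a reader cannot separate the two and has to go back to the listings. The tables are small, so one such patient is visible in the percentages.

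**Working it through.** The SAP gives no figure for this analysis, so there is none to reproduce. The check has two parts: what the wider term adds, and what one added patient does to each table.

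**What AE adds to TEAE.** Apply the 6.7.1 definitions to an injury of known onset, with one dose and therefore one predose/postdose boundary:

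| Injury onset | More severe postdose? | AE | TEAE |
|---|---|---|---|
| Before consent, ongoing | No | Yes (pre-existing) | No |
| Before consent, ongoing | Yes | Yes | Yes |
| Consent to dose | No | Yes | No |
| Consent to dose | Yes | Yes | Yes |
| Postdose | n/a | Yes | Yes |

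AE minus TEAE leaves the first and third rows only. The first counts only if pre-existing conditions are read literally as AEs.

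**Order.** Set the dose at time 0. An added injury has onset t(I) < 0. The onset or worsening that makes a neurologic event a TEAE has t(N) ≥ 0. So t(I) < t(N) in every case, and no added injury can follow that onset or worsening.

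**Predose window (context only).** SAP 5.1 puts screening 28 to 3 days before dosing and follow-up about 14 days after. Assume consent at screening, a constant background injury rate and no postdose worsening. The predose share of injuries with onset between consent and follow-up is then 3/(3 + 14) = 3/17 = 18% to 28/(28 + 14) = 28/42 = 67%. This is a ratio of calendar time, not an effect on any table, and it leaves out injuries that began before consent.

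**First summary.** SAP 5.2 plans about 13 patients in Cohort 1 and about 8 in Cohort 2, so 13 + 8 = 21. Assume all are dosed and form the denominator. One patient whose only injury is predose raises the injury line by:

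- 1/21 = 4.8 points overall
- 1/13 = 7.7 points if in Cohort 1
- 1/8 = 12.5 points if in Cohort 2

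**Second summary, preferred-term rows.** The denominator is the group with at least one injury AE, so the added patient enlarges it. Assume two patients with treatment-emergent injuries, one with term A and one with term B: each row is 1/2 = 50%.

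- Added patient has a new term C: A and B each become 1/3 = 33%, and C appears at 1/3 = 33%.
- Added patient has term A: A becomes 2/3 = 67% and B becomes 1/3 = 33%.

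**Second summary, cross-tabulation.** The SAP states no denominator. Assume it is the patients with that term.

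- Different term: the added patient forms a new row (1/1 or 0/1) and other rows do not change.
- Same term: an assumed 1/2 = 50% becomes 2/3 = 67% if the added patient has a neurologic TEAE, or 1/3 = 33% if not.

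**The case against.** **A wide net may be deliberate.** Section 6.7.8.3 uses AE for injuries and TEAE for neurologic events throughout, and a broad search followed by medical judgement is a pattern in this SAP. Section 6.7.8.1 searches both TEAEs and AEs for cardiovascular terms, and 6.7.8.4 and 6.7.8.7 use plain AE. Intent therefore cannot be excluded. But 6.7.8.1 says expressly that it wants both, and the other two sections use AE to select patients for narratives, where each case is read. Section 6.7.8.3 makes no such statement about its counts.

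**Medical review settles relatedness.** This largely stands and is why the point is minor. The planned study is about 21 single-dose patients, 6.7.10 plans no inference, and the listings show every AE. However, the timing condition in 6.7.8.3 governs the review and not the tables.

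**TEAE on both sides does not establish order.** This stands. A postdose injury can still precede the neurologic TEAE.

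**Switching to TEAE creates a missing-onset problem.** This also stands. As written, AE counts an injury with no start time without needing a rule. The 6.7.1 definitions cannot place such an event, 6.2 gives no default, and the missing-time exclusion in 6.7.8.5 covers only the abuse-liability onset and duration analyses. A default set in 6.7.8.3 alone would conflict with the 6.7.1 TEAE tables.

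**The TEAE window may be limited in time.** Section 6.7.8.7 calls non-TEAEs non-immediate reactions, which would suit such a window. AE would then also pick up late postdose injuries. The SAP states no such window and the 6.7.1 definition is explicit, so this is a separate inconsistency to reconcile.

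**Conclusion.** The point holds as a minor one, worth considering. Among injuries of known onset, AE in place of TEAE adds only predose, non-worsened injuries, and these do not serve the section's stated purpose. The documents give no injury or neurologic event rates, so the number of patients affected cannot be computed and may be nil. The sizes shown for one patient (4.8, 7.7 or 12.5 points) rest on the planned enrolment and on all enrolled patients being dosed. The second-summary figures rest on assumed counts.

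A reader might infer more than this. Four stronger readings are not supported:

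- *Every added injury is unrelated to any neurologic event.* It could follow the predose phase of a neurologic event that later worsened. It cannot follow the part that makes that event a TEAE.
- *The plan misses drug-related injuries.* AE contains TEAE, so the fault is over-inclusion only.
- *The safety conclusions are unsound.* The listings, medical review and narratives do not depend on these counts.
- *The same fault applies to the repeat-dose addendum.* The reasoning rests on the single dose in the SAP and was not extended to the addendum.

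**What to change.** 1. In both 6.7.8.3 summaries, use TEAE for the Injury, Poisoning, and Procedural Complications class. No injury with known postdose onset or worsening is lost. If a wide net is intended, keep AE, say so, and show treatment-emergent and predose injuries in separate columns.
2. State once, in 6.7.1, that an AE whose onset cannot be placed before dosing (for example, a dosing-day event with no start time) counts as treatment-emergent. All TEAE tables then agree, and either version of item 1 can be programmed.
3. Add a footnote that the cross-tabulation shows co-occurrence within a patient and not the order of onset.

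Listings, medical review and narratives stay as they are, so predose injuries remain visible there.

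The cost is SAP wording, a filter or one extra column, and a default that applies to all TEAE tables. The downside is that an AE with no start time that was in fact predose would be counted as treatment-emergent.

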6.7.8.4. Road Traffic Accidents

Patient narratives for patients who reported AEs with PTs of road traffic accident, impaired ability to use machinery, or accident, will be provided.

6.7.8.5. Drug Abuse Liability Evaluation

With 2 exceptions described below (SMQ of Drug abuse and dependence, listing of patients with reported overdose AEs), all analyses to evaluate abuse potential will only be performed in patients 12 to <18 years of age.

The following event clusters will be used to evaluate potential abuse liability:

- The SMQ of Drug abuse and dependence [20000101], including individual PTs, all narrow terms, and all (narrow and broad) terms. This will also be done separately in patients 6 to <12 years of age.

- The LSC of “Additional potential abuse liability” terms. This LSC contains additional terms based on Food and Drug Administration guidance (FDA 2017 [WWW]) that are not included in the Drug abuse and dependence SMQ, including terms for Dissociation/psychotic, Euphoria, Impaired attention, Cognition and mood, and Other abuse-related terms. Summaries will be provided at the PT level and the overall level.

The term list is based on the most current MedDRA version and is provided in [Appendix 2](#).

The analyses in this section will include a total count of patients experiencing TEAEs from the above search and will be listed by SMQ or LSC Additional potential abuse liability terms, and then sorted by decreasing frequency in the total population within each SMQ or LSC Additional Terms group. For the SMQ, a summary will also be provided at the narrow and broad level. For both the SMQ and LSC Additional potential abuse liability terms list, each PT will be summarized. Additionally, the overall number (the number and percent of patients who experienced any TEAE from the above search) will be analyzed.

Patient narratives of possible abuse related events (time of onset and duration of event, dose of drug, severity and outcome) will be provided.

The following additional analyses will be performed:

- Times to onset and durations of TEAEs which may represent a sign of abuse liability (AL) will be summarized for individual abuse potential terms and any AL term.
- Onset times relative to first dose and durations of AEs for patients with at least 2 AL TEAEs will be plotted for any abuse potential AEs for these patients.
- Onset/duration plots (see [Appendix 3](#)) by cohort for each AL TEAE. In the event that 1 or more AL TEAEs occur in a disproportionate percentage of the population, this analysis will exclude those terms.

All the time to onset analysis will exclude events that are missing event start times/dates or missing dosing times/dates, and all duration analysis will exclude events that are missing event start or stop times/dates or missing dosing times/dates.

Descriptive statistics will be presented separately by body weight category and age category.

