5.1. Summary of Study Design

This is a Phase 1, multi-center, open-label, single dose study to determine the pharmacokinetic (PK), safety, and tolerability of lasmiditan in pediatric patients with a diagnosis of migraine.

Two cohorts will be evaluated:

- Primary **Cohort 1**: 15 kg to ≤ 40 kg
- Secondary **Cohort 2**: >40 kg to ≤ 55 kg

The planned doses for Cohorts 1 and 2 are 100 mg and 200 mg, respectively.

Study Period I (Screening)

All patients are screened to determine if they are eligible to participate in the study.

Screening will occur 28 days to 3 days prior to lasmiditan dosing.

Study Period II (PK Assessment/Safety)

Enrolled patients and the patient's parent or guardian will receive instructions regarding study procedures prior to dosing, including fasting requirements.

Day 1:

- Patients arrive at the Clinical Research Unit (CRU) for assessments prior to dosing.
- Patients receive the single lasmiditan dose.
- Patients can go home after the 12-hour assessments. Patients may be offered the opportunity to spend the night depending on CRU capabilities.

Day 2:

- Patient assessments are done at the CRU approximately 24 hours after dosing.

Study Period III (Follow-Up Period)

Patients return to the CRU for a follow-up visit approximately 14 days after dosing.

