6.2. Handling of Dropouts or Missing Data

Missing data will not be displayed in listings.

Some of the tables, figures, and listings (TFLs) may not have sufficient numbers of patients or data for presentation. If this occurs, the blank TFL shell will be presented with a message printed in the center of the table, such as, “No serious adverse events occurred for this study”.

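### Dropping abuse-liability events that have no stop time removes events still ongoing at last contact and biases the descriptive duration summaries short

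*SAP*

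**What the plan says.** SAP section 6.7.8.5 plans two kinds of duration output. "Times to onset and durations of TEAEs which may represent a sign of abuse liability (AL) will be summarized", both for each abuse-potential term and for any such term. There are also onset/duration plots "by cohort for each AL TEAE", and a plot for patients with at least two such events. The section closes with the rule that "all duration analysis will exclude events that are missing event start or stop times/dates or missing dosing times/dates".

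The rule makes no exception for an event that has not resolved. Section 6.2, the general section on missing data, gives no censoring or imputation rule for ongoing events; its only rule for missing values is "Missing data will not be displayed in listings". Nothing asks for a count of the events left out.

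Follow-up is short: "Patients return to the CRU for a follow-up visit approximately 14 days after dosing" (SAP section 5.1). The population is small. Section 5.2 plans about 13 + 8 = 21 patients, and with two exceptions "all analyses to evaluate abuse potential will only be performed in patients 12 to <18 years of age".

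**The concern.** The closing rule of 6.7.8.5 treats three situations alike. Without a start time, a duration can be neither calculated nor bounded. For a resolved event whose stop time was not recorded, the end is unknown. An ongoing event is different: its duration is known to exceed the time from its start to last contact. Dropping it discards that information and leaves only events that resolved within follow-up. This is a complete-case analysis of right-censored data.

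The question behind these tables is how long possible abuse-related and central nervous system effects last. The Appendix 2 list includes terms such as anxiety, irritability, fatigue, headache and decreased appetite, which can outlast a Day 14 visit even if acute sedation clears quickly. Durations are summarised per term and then split by body weight and age category, so many cells may hold one or two events. A term whose only event is ongoing would have no duration at all.

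**Working it through.** The plan states no figure for event durations, so there is none to reproduce. The inputs from the documents are the exclusion rule (SAP 6.7.8.5) and follow-up of about 14 days, or 14 × 24 = 336 h, after dosing (SAP 5.1). The share of events ongoing at last contact and the distribution of durations are not given; everything on those below is an assumption, shown over a range.

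**Direction.** Let D be the true duration and A the time from onset to last contact. The rule keeps an event only if D ≤ A. If duration is unrelated to onset time, the chance of being kept, P(A ≥ d), cannot rise as d rises. Long events are therefore kept less often, and the retained durations are shifted short. The shift cannot reverse under that condition.

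**Size, onset at dosing.** For exponential durations with true mean m days and 14 days of follow-up:

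- share dropped = exp(−14/m)
- mean of retained events = m − 14·exp(−14/m) / (1 − exp(−14/m))

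For m = 7: exp(−2) = 0.1353, and the retained mean is 7 − 14 × 0.1353/0.8647 = 4.81 days.

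**Size, later onset.** With onset spread evenly over the 14 days, the share dropped is (m/14)(1 − exp(−14/m)). The retained means in that column come from a simulation of 2,000,000 events per scenario.

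| True mean | Onset at dosing: dropped | Retained mean | Onset spread over 14 days: dropped | Retained mean |
|---|---|---|---|---|
| 6 h (0.25 d) | 0.0% | 0.25 d | 1.8% | 0.245 d |
| 1 d | 0.0% | 1.00 d | 7.1% | 0.92 d |
| 3 d | 0.9% | 2.87 d | 21.2% | 2.23 d |
| 7 d | 13.5% | 4.81 d | 43.2% | 3.34 d |
| 14 d | 36.8% | 5.85 d | 63.2% | 3.95 d |

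In the 7-day case with onset at dosing, the median falls from 4.86 to 3.96 days.

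**Mostly short events with a few long ones.** Suppose 95% of events have a mean of 6 h and 5% a mean of 30 days, with onset at dosing (simulated). Then 3.1% are dropped. The mean falls from 1.73 to 0.37 days, while the median hardly moves (0.187 to 0.178 days).

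**A table of realistic size.** Take seven resolved events of 2, 3, 4, 6, 8, 12 and 24 h, and one ongoing at the Day 14 visit.

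- Planned rule: mean 59/7 = 8.4 h, median 6 h, maximum 24 h, with no sign of an eighth event.
- Ongoing event kept as censored: the Kaplan-Meier curve equals 4/8 = 0.5 between 6 and 8 h, so the median is 7 h by the midpoint convention.
- If the ongoing event began at dosing it has lasted more than 336 h, and the mean of the eight is at least (59 + 336)/8 = 49.4 h. If it began 312 h after dosing it has lasted more than 336 − 312 = 24 h, and the mean is at least (59 + 24)/8 = 10.4 h.

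The 336 h figure is time since dosing. It is the length of an ongoing event only when onset coincides with dosing.

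**Censored time is not a completed duration.** In the 7-day case with onset at dosing, averaging the observed time for all events gives 6.06 days against a true mean of 7. This is why the fix uses `>x` values and a Kaplan-Meier median rather than a plain mean that includes ongoing events.

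**The case against.** The strongest reply is that the rest of the safety reporting still shows a persistent event. Section 6.7.8.5 itself requires that "Patient narratives of possible abuse related events (time of onset and duration of event, dose of drug, severity and outcome) will be provided". Section 6.7.1 provides for listing of "All AEs occurring on or after the date of informed consent form signing". The patient counts of abuse-liability TEAEs do not depend on a stop time. Section 6.7.10 plans no inferential analysis, and the primary objective is pharmacokinetic. All of this stands, and it limits the harm. A reader might infer that the safety evaluation as a whole conceals lasting effects; the documents do not support that. What remains is that the table and plots are planned outputs in their own right, and nothing links them to the narrative of an event they have omitted.

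Three further objections have force:

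- The SAP does not say in so many words that an ongoing event counts as missing its stop time, and the Appendix 3 mock plots, which might show how such events are drawn, were not visible in the text I had. However, an unresolved event has no stop time to record, and the rule contains no exception, so a programmer following it would drop the event.
- It is tempting to say that the rule removes the longest events. That goes too far. A late-onset event can be ongoing and still fairly short. In the simulations with onset spread over follow-up, 85% to 96% of dropped events were longer than the retained median, not all of them.
- It is also tempting to keep every event that lacks a stop time. That would be wrong, because censoring a resolved event at last contact when its end was merely unrecorded would overstate how long it lasted.

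**Conclusion.** The point holds as a minor one. Followed as written, the rule biases the abuse-liability duration summaries and plots short whenever an event is still ongoing at last contact. The direction rests on duration being unrelated to onset time.

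The size cannot be established from the documents. It is near zero if events resolve within hours to a day of an early onset. It is material, chiefly for the mean and maximum, if any event persists to the Day 14 visit. The median moves little when few events are dropped. The durations and onset patterns used above are assumptions; nothing in the documents shows that any event will last that long.

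The distortion stops at descriptive duration output. It does not reach TEAE counts, listings, narratives or the pharmacokinetic results. It applies to the single-dose study that this SAP covers; neither document specifies a duration analysis for the open-label addendum.

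**What to change.** Amend the closing rule of SAP section 6.7.8.5 to separate the reasons for a missing stop time:

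- **Events recorded as ongoing at last contact:** keep them as right-censored, with duration equal to last contact minus event start. Show them as `>x` in the summary, mark them in the onset/duration plots, and report how many there are. Give a Kaplan-Meier median only where event numbers allow; with about 21 patients planned, many individual terms will need only the `>x` values.
- **Events with a missing start or dosing time, and resolved events whose stop time was not recorded:** continue to exclude them, and report their number separately from the ongoing events.

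The cost is slightly more programming and one extra table column. The calculation needs only the event start, the ongoing status and the last-contact date. If every event resolves with a recorded stop time, the duration results are the same as under the present rule.
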